1 INTRODUCTION / BACKGROUND & RATIONALE

incident pregnancy.

Hypertensive disorders complicate 6-12% of pregnancies (Khedagi and Bello 2021), leading to PE and intrauterine growth restriction (Di Martino et al. 2022). PE is more commonly associated with adverse maternal and foetal outcomes such as eclampsia, stroke, renal and hepatic dysfunction, foetal growth restriction and stillbirth. According to the most recent Confidential Enquiries into Maternal Death, PE is still one of the most common causes of direct maternal deaths in United Kingdom and is also associated with increased perinatal mortality and morbidity(Shennan et al. 2012). GH is increasing in line with elevated cases of obesity and diabetes in the population (Shah et al. 2008). This is becoming more critically relevant for maternity especially as the obese and diabetic population is increasing in the younger age groups during the reproductive. Hypertensive disorders in pregnancy account for 5% (1:20) of stillbirths with no congenital malformation. Importantly, women who develop PE are also at increased long-term risk of CV disease and stroke (Honigberg et al. 2022). The impact of increased risk of CV disease later in life is under appreciated. Predictions of pregnancies at risk of hypertensive pregnancy will allow stratification of women at most risk, for future and earlier follow up. In addition, this understanding will provide insight into pathological mechanisms. An understanding of when endothelial dysfunction occurs and if it preceeds gestational hypertension will be key to developing diagnostic stratification. Recent studies have suggested that arterial stiffness and endothelial dysfunction may be an important factor in development of GH. Similarly, myocardial impairment and chamber diastolic dysfunction was observed more frequently in GH (a severe form of GH compared with normal pregnancies. These changes in CV function may be present before the clinical onset of GH and are evident after delivery. Therefore, GH seems to be the expression of a

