3.2 STUDY RECRUITMENT

Women will be recruited who are pregnant for assessment in mid and/or late term. The outcome of the pregnancy will be tracked.

Women will be invited to join the study by the care teams in clinics at Ninewells and the Tayside area

- Obstetric Antenatal Clinics (Recruitment will be overseen [name] [name] (UoD/NHS) and [name] (NHS))
- Assisted conception clinic (Recruitment will be overseen [name] [name] (UoD/NHS))
- Hypertension Clinic (Recruitment will be overseen by [name](UoD/NHS))

This is a prospective study. Control groups will be made up of women that do not get gestational hypertension. Pregnant women that attend the Hypertension clinic may be recruited due to their gestational hypertension. Women attending the Obstetric Antenatal Clinics and Assisted conception clinics will be identified with clinical collaborators including [name] [name], [name] and [name]. To be able to identify potential participants from their medical records Caldicott Approval will be sought. Only with Caldicott approval will the medical records be searched.

The care team will approach or invite participation in the study in clinic. Any invitation will introduce the potential patient to the study team and will include a PIS. The care team will not follow up with patients to determine their interest in the study.

The study team will include Clinical Research Centre nurses that will assist with recruitment. The study team will confirm recruitment via a short telephone conversation prior to them attending Ninewells for the study visit.

Advertisement of the study and identification of potential participants will be identified from the NHS Tayside clinics at Ninewells Hospital including maternity clinics, ultrasound department, antenatal clinics, day assessment unit, Assisted Conception Unit, https://www.acudundee.org/ hypertension and diabetics clinics among others. Caldicott approval will be gained to allow identification of potential participants from medical records and clinical lists by the care team. Letters with PIS may be sent to the potential participants from the clinical team. We chose the following sites, since this is where pregnant women obtain their routine care.

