6.1 SAMPLE SIZE CALCULATION

Comparison of CV function in women at high and low risk of PE

Ninewells has approximately 4500 births per year with approximately 450 cases of gestational hypertension. Our goal here is to describe the evolution of maternal microvascular function in women that develop gestational hypertension comparing to those that do not develop gestational hypertension.

Our previously published studies (Khan et al 2005 Hypertension, https://doi.org/10.1161/01.HYP.0000186328.90667.95; Changes in Endothelial function preceded the clinical disease in women in whom PE develops) demonstrated changes in microvasculature at 26 weeks in n=15 women with PE compared to normotensive (n=54). Using this previous data, a Power Analysis (G*power)) -A Piori carried out to compute the required sample size for the Wilcoxon-Mann Whitney test (2 groups). With

αα

= 0.05 and power of 95% to detect an effect size of 25%, each group requires a n=11.

As this is a prospective study to obtain measurements at the onset of gestational hypertension, we predict we need to recruit 110 women to obtain the 10% of women that develop gestational hypertension. Women who are high-risk or that have been newly diagnosed, i.e. attending hypertensive clinics, will be recruited

Further details:

 During-Pregnancy: Recruit 110 women to account for the 10% who will develop gestational hypertension.

Sample size required for each group (high vs. low risk):11 women per group

• Total Participants:

-During-Pregnancy: 110 women (recruitment to achieve the final sample of 22 women)

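### The 110 recruits in 6.1 rest on the all-births 10% incidence, yet high-risk and already-diagnosed women are also recruited, so 110 does not follow and the case group can mix measurements from before and after onset

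*Protocol*

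**What the plan says.** Section 6.1 takes its incidence from local figures: "Ninewells has approximately 4500 births per year with approximately 450 cases of gestational hypertension". The power calculation concludes that "each group requires a n=11". The recruitment total follows: "we predict we need to recruit 110 women to obtain the 10% of women that develop gestational hypertension". The next sentence widens the intake: "Women who are high-risk or that have been newly diagnosed, i.e. attending hypertensive clinics, will be recruited". The closing list in 6.1 gives 110 as the during-pregnancy total, recruited to reach a final sample of 22.

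Other sections agree with the wider intake. Section 3.2 says: "Pregnant women that attend the Hypertension clinic may be recruited due to their gestational hypertension". Section 3 lists two streams, pregnant women followed to outcome and women who already have GH with gestation-matched normotensive women. Section 3.14 defines a case as a woman diagnosed with GH in this pregnancy. Section 3.12, in contrast, enrols all pregnant women and assigns groups afterwards by outcome. Sections 3.3 and 3.5 accept a single visit.

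On purpose, section 3 relates endothelial function to the later development of GH, and 6.1 aims to describe microvascular function in women who develop it. The background adds: "An understanding of when endothelial dysfunction occurs and if it preceeds gestational hypertension will be key".

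**The concern.** Dividing 11 by 10% is right only if every recruit has a 10% chance of becoming a case. A woman recruited because she has GH has a chance of 1, and a high-risk woman presumably has more than 10%. Section 6.1 uses the 10% and in the next sentence admits both kinds of women, without a number, share or cap. The figure and the recruitment rule therefore do not belong to the same study.

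The larger stake is what the case group will contain. A case imaged after diagnosis shows how the vessels look once GH is present. A case imaged before diagnosis bears on whether change comes first. Both count towards the same 11, and nothing sets a minimum for the second kind. A pooled result could be read as evidence that vascular change precedes or predicts GH when many of the cases were imaged afterwards.

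**Working it through.** **Inputs.** From 6.1: 4500 births and 450 GH cases a year, 11 cases needed, 110 recruits. The protocol does not give the number of already-diagnosed women (h) or the incidence in high-risk women, so both are assumptions shown over a range.

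**The plan's own figure.** Incidence = 450/4500 = 0.10. Recruits = 11/0.10 = 110. This reproduces exactly, for unselected women with no diagnosed case at entry.

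**Adding diagnosed women.** With h diagnosed among 110 and 10% of the rest becoming cases:
- expected cases in 110 = h + 0.10 × (110 − h)
- recruits for 11 expected cases = h + (11 − h)/0.10

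| h (assumed) | Expected cases in 110 | Of these, arising after enrolment | Recruits for 11 expected cases |
|---|---|---|---|
| 0 | 11.0 | 11.0 | 110 |
| 5 | 15.5 | 10.5 | 65 |
| 8 | 18.2 | 10.2 | 38 |
| 11 | 20.9 | 9.9 | 11 (cases only; controls come on top) |

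**Adding high-risk women.** If nobody is diagnosed at entry but incidence is 20%, 11/0.20 = 55 recruits suffice and 110 would give 22 expected cases. At 30%, 11/0.30 is about 37, and 110 would give 33.

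**Mix within the case group.** Take women enrolled before diagnosis as imaged before it. The pre-onset share of cases is then 10.5/15.5 = 68% at h = 5 and 9.9/20.9 = 47% at h = 11. In a case group of 11, the latter is about 5 women.

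**Certainty of reaching 11 without diagnosed women.** With 110 recruits at 10% incidence, the exact binomial probability of 11 or more cases is 0.546. An 80% chance needs 135 recruits and a 90% chance needs 152. The 110 is an expected-value figure with no margin.

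**The case against.** A reader might infer that the 11 case places could fill entirely with diagnosed women, leaving nobody imaged before onset. The documents do not support this as the expected course. It requires recruitment to stop at the 11th case, and no section states such a rule. The 22 in 3.13 can be read with 6.1 as the final sample drawn from 110. If 110 are recruited with 11 already diagnosed, 9.9 incident cases are still expected among the other 99. The chance of none at 10% is 0.9^99, about 0.00003.

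A reader might also infer that the study is too small. On case numbers the reverse holds: enrichment makes 110 more than enough for 11 cases.

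The strongest defence is that including diagnosed women is deliberate. Sections 3, 3.2 and 3.14 provide for them, Table 1 sets the timepoint as mid-to-late pregnancy in women with GH and normal pregnancies, and 6.1 itself speaks of measurements at onset. This stands: the GH versus normal comparison can use them, and barring them would contradict those sections.

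Some limits on their number also exist. The synopsis excludes women on ongoing anti-hypertensive therapy. The visit windows in 3.5 (weeks 10 and 20, each ± 3) end near week 23, while 9.1 defines GH as arising after week 20. However, 3.2 and 3.14 allow mid and late pregnancy, so these limits reduce the mixing without preventing it. Section 6.1 also does not say outright that clinic recruits count within the 110, although its total of 110 favours that reading.

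**Conclusion.** The point holds in a limited form. The 110 is correct arithmetic for a recruitment that the protocol does not describe. With the intake it does describe, 110 women would be expected to give more than 11 cases: 15.5 with 5 diagnosed women and 20.9 with 11, if 10% applies to the rest. The exact excess cannot be stated because the mix is not given.

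The consequence is one of interpretation rather than of too few cases. The case group can combine pre-onset and post-onset measurements in unplanned proportions, with no minimum of pre-onset cases, although section 3 and 6.1 are directed at women who develop GH. This should be corrected before recruitment, but it does not undermine the mid-to-late pregnancy comparison of GH with normal pregnancy.

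**What to change.** 1. In 6.1, state that 110 applies to women enrolled before any GH diagnosis, with 11 incident cases expected at 10% and only about a 55% chance of 11 or more. If high-risk women are among them, state the incidence assumed for them.
2. In 6.1, give the planned number of already-diagnosed women separately, and say whether they are additional to the 110.
3. Reconcile these numbers with the sample-size entry of 44 in the synopsis (if that is a participant count) and the 22 in 3.13 and 11.2. Align 3.12 and 3.14 on how cases enter.
4. Record on the CRF whether each woman was imaged before or after GH diagnosis.
5. Keep diagnosed women in the mid-to-late pregnancy comparison, but report the two case types separately. Base any statement that vascular change precedes or predicts GH only on women imaged before diagnosis.

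The cost is some rewording and one CRF field. The drawback is that the pre-onset question will rest on fewer cases than the pooled group, and a shortfall from 11 may have to be reported. Recruiting 152 women before diagnosis would raise the chance of 11 incident cases to 90%, if the sponsor wants that assurance.

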3.13 NUMBER OF PARTICIPANTS

Study: 22 PARTICIPANTS
11 participants for case group
11 participants for control group

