11.2 STUDY RECORD RETENTION

No NHS medical case notes will be retained. Archiving of study documents will be for five years after the end of study or in the case of anonymised data will be retained for 15 years.

We will only be collecting data that is specifically required for the project. We will be collecting data from ~22 participants.

Studying Pregnancy's VAscular and Retinal Changes (SPARC), Non CTIMP Protocol (SPARC) During Preg <v1.0 13/3/2025>; IRAS: 347685

Data will be anonymised and retained for 15 years, in requirement of publishing results from the study.

University guidelines and IT department will be provide the adequate procedures to securely delete personal data. Health Informatics Centre will provide advice and support to anonyomize the data and provide the means to securely retain the code for a limited period (5 years).

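### The protocol's participant numbers conflict (110 recruited, 22 studied), no procedure selects 11 controls from about 99, and 110 is only the expected-value target for 11 cases

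*Protocol*

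**What the plan says.** **Numbers.** Section 6.1 ends with "110 women (recruitment to achieve the final sample of 22 women". Section 3.13 reads "Study: 22 PARTICIPANTS", split into 11 cases and 11 controls. Section 11.2 reads "We will be collecting data from ~22 participants". The synopsis sample-size row contains only P. 44.

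**Per-group size.** Section 6.1 sizes the study for a Wilcoxon-Mann-Whitney test: "0.05 and power of 95% to detect an effect size of 25%, each group requires a n=11". It repeats this as "Sample size required for each group (high vs. low risk):11 women per group".

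**Recruitment target.** The rate comes from local figures: "Ninewells has approximately 4500 births per year with approximately 450 cases of gestational hypertension". From it, "we predict we need to recruit 110 women to obtain the 10% of women that develop gestational hypertension". The same paragraph adds that high-risk or newly diagnosed women from hypertension clinics will also be recruited, without saying how many.

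**Who is a control.** Section 3.2 forms the control group from women who do not get GH. Section 3.12 takes in all eligible pregnant women at the start and assigns them to groups retrospectively, once the outcome is documented. Section 3 separately lists recruiting women with GH and gestation-matched normotensive women. Sections 3.2 and 3.14 also allow for women who already have the diagnosis.

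**The concern.** The number of women consented, imaged and bled is a basic statement on which sponsor, ethics and R&D approvals rest. Here it differs fivefold between sections. Section 6.1 does disclose 110 and links it to 22, but 3.13 and 11.2 mention only 22, and 11.2 says so specifically about data collected.

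The link between 110 and 22 is also incomplete. If every woman without GH is a control, 22 is the wrong analysed number. If only 22 are analysed, 11 controls must be chosen from about 99, possibly after outcomes and measurements are known, with no stated procedure. That leaves room for selection and gives up precision already paid for.

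Finally, the recruitment target carries no allowance for chance or loss, so 11 cases is presented as a result of recruiting 110 when it is only the average result.

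**Working it through.** **Inputs, all from section 6.1:** 11 per group; alpha 0.05; Mann-Whitney test; 450 GH cases in 4500 births. Sidedness is not stated, so two-sided is assumed below.

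**1. The recruitment figure reproduces.** Rate = 450/4500 = 0.10. Recruits = 11/0.10 = 110.

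**2. What 110 recruits produce at that rate.** Cases: 110 × 0.10 = 11. Controls under 3.2 and 3.12: 110 − 11 = 99. Women outside a final sample of 22: 110 − 22 = 88.

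**3. Chance of reaching 11 cases.** Cases ~ Binomial(n, p); P(X ≥ 11):

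| Scenario | P(at least 11 cases) |
|---|---|
| n = 110, p = 0.10, no loss | 0.546 (2.5 to 97.5% range 5 to 18) |
| 10% loss (assumed), n = 99, p = 0.10 | 0.404 |
| n = 110, p = 0.06 | 0.066 |
| n = 110, p = 0.12 | 0.782 |
| n = 110, p = 0.15 (assumed) | 0.952 |
| 3 of the 110 already diagnosed (assumed), other 107 at 0.10 | 0.850 |
| 5 of the 110 already diagnosed (assumed), other 105 at 0.10 | 0.958 |

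The 6% and 12% rows use the range that section 1 gives for all hypertensive disorders of pregnancy. With unselected women at 10% and no loss, at least 11 cases would need 135 recruits for an 80% chance, 152 for 90% and 167 for 95%.

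**4. Precision of the group difference.** In units of a common SD, SE = √(1/n₁ + 1/n₂). Detectable standardised differences and power use a noncentral t approximation with Mann-Whitney efficiency 3/π = 0.955.

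| Cases v controls | SE (SD units) | Detectable difference, 80% power | Detectable difference, 95% power | Power at 1.0 SD |
|---|---|---|---|---|
| 11 v 11 | 0.426 | 1.29 | 1.66 | 59% |
| 11 v 44 | 0.337 | 0.99 | 1.27 | 81% |
| 11 v 99 | 0.318 | 0.92 | 1.18 | 86% |

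SE ratio, 11 v 99 to 11 v 11: 0.318/0.426 = 0.745, about 25% smaller. If the case SD were 1.5 times the control SD (assumed), the ratio is √(2.25/11 + 1/99) / √(2.25/11 + 1/11) = 0.852, about 15% smaller.

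**5. Correlations (section 6.2).** Fisher z at 80% power: r = tanh[(1.960 + 0.842)/√(n − 3)]. For n = 22, r = 0.57; for n = 110, r = 0.26. This takes all women as one sample.

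**The case against.** **Are about 88 imaged controls thrown away?** A reader might infer this from the phrase about a final sample. The documents do not establish it. No section says any woman is dropped, 3.2 and 3.12 read as if every woman without GH is a control, and 6.2 does not restrict the correlations to 22. Section 11.2 can even be read as saying that only about 22 women have data collected. What stands is the contradiction.

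**Is group always unknown at assessment?** No. Sections 3, 3.2, 3.14 and 6.1 also recruit women already diagnosed, alongside matched normotensive women. The protocol mixes a cohort with case-control recruitment, so it is not settled that all 110 must be measured before anyone is classified.

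**Is there no selection rule at all?** Gestational matching is named in section 3. It lacks a ratio, a timing and a procedure.

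**Is 11 cases a coin-toss?** Only for 110 unselected women at 10% with no loss. Section 6.1 plans enrichment, and a few directly recruited cases change the answer markedly. The 55% is therefore not a forecast for the planned cohort.

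**Would using all controls be a free gain?** Not automatically. Section 3.5 accepts a single visit near week 10 or week 20 (±3 weeks), 3.14 wants cases in mid-to-late gestation, and 9.1 places GH after 20 weeks. Pooling controls without regard to gestation could confound group with gestational age.

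**Is 44 a third sample size?** Possibly, but P. 44 may be a page reference.

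**Conclusion.** The point holds as a contradiction in a core design number, with an unfinished control-selection plan and a target set at its expected value. The figures 110 and 22 cannot both be the number of women studied. If P. 44 is a participant count, it matches neither.

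At the protocol's own 10% rate the gap is about 88 women. Including the eligible controls among them would cut the standard error by up to about 25%. That is an upper figure, assuming equal variances, exactly 11 cases and 99 comparable controls.

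The 55% chance of at least 11 cases is correct arithmetic on the stated rate, conditional on no enrichment and no loss. The true chance could be well above or below it, and the protocol gives nothing from which to tell. The documents do not support saying that measured controls are definitely discarded, or that the planned study has only an even chance of 11 cases.

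**What to change.** 1. State one number recruited and assessed, and one number analysed, and use the same pair in the synopsis, 3.13, 6.1 and 11.2. Clarify or remove P. 44.
2. Analyse all eligible assessed controls. Handle gestational age at assessment by adjustment or by restricting to comparable visit windows.
3. If assay capacity limits numbers, pre-specify a gestation-matched nested sample, for example 4 controls per case, drawn without sight of the imaging, Doppler or biomarker values. With 11 v 44 the detectable difference at 95% power is 1.27 SD, close to the 1.18 SD for all controls.
4. Describe 11 cases as the expected count conditional on a 10% rate. Give separately the number expected from direct recruitment of diagnosed women, and state any allowance for loss. A range of 5 to 18 should appear only with its condition attached, because it does not describe an enriched cohort.

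The cost is wording, slightly more analysis and possibly more assays, which the nested option limits. None of these changes in itself requires recruiting beyond 110.

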6.2 PROPOSED ANALYSES

- **Study
- **Aim**: To investigate correlations between retinal imaging, ultrasound and blood sample biomarkers and future CVD risk factors in mid-late stages of gestation.
 - Hypothesis:

Cardiovascular Assessment:

Blood biomarker (sFlt-1, PIGF)) will correlate with retinal vascular changes and Dopple rultrasound indices, potentially predicting future CVD.

- **Methods**:
- Perform *correlational analysis* between retinal metrics and blood biomarkers to examine associations.
- Conduct *logistic regression analyses* to assess whether retinal imaging metrics in early pregnancy predict future CVD risk.
- *Multivariable regression modeling* to control for confounding factors such as maternal age, BMI, and pre-existing health conditions.

Data Protection Impact Assessment (DPIA)

- We aim to understand the link between retinal imaging biomarkers and cardiovascular function in gestational hypertension, predicting CVD risk factors and informing early interventions.

What will be the effect on data subjects?

-Positive Impact**: Early detection of risk factors for cardiovascular health, potentially improving maternal health management and long-term care.

What is the nature of the University's relationship with the data subjects?

- The University serves as the primary researcher and data controller, conducting the study with informed consent from participants. The relationship is one of informed, voluntary participation in medical research.

Are they expecting you to use their data in the way you've proposed?

- Yes, participants are fully informed through the consent process about the study's objectives, data collection, and how their data will be used for research on maternal and cardiovascular health.

Are there prior concerns with this proposed activity in the public domain that you are aware of?**

- Retinal imaging and biomarker studies in maternal health are generally well-accepted, though concerns about the use of sensitive medical data highlight the importance of rigorous data protection.

Is the University signed up to any codes of conduct in respect of the data processing?

- The University adheres to all GDPR guidelines and maintains compliance with institutional data protection policies, ensuring ethical handling and storage of sensitive health data.

Are there sufficient resources to meet the data security requirements for this type of processing?

- Yes, the University has sufficient resources to meet data security needs, including secure data storage, access control, and compliance checks to protect participants' data throughout the study.

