Primary	Objectives To investigate the potential of retinal imaging technology to assess endothelial function in women during pregnancy, in order to evaluate the effect of GH on maternal CV function.	Outcome Measures Primary Outcome Measures: 1. Retinal Vascular System 2. Endothelial Function 3. Cardiovascular Function biomarkers Secondary Outcome Measures: 1. Pregnancy-Related Health Outcomes 2. Maternal Health
Secondary	Objectives Study – Aim: Investigate whether retinal imaging is able to capture endothelial dysfunction in women who have complicated pregnancy. Endothelial function measured using retinal imaging and ultrasound pulse-wave Doppler and measured in correlation with serum biomarkers.	Outcome Measures 1. Primary Outcome Measures - Retinal Vascular Health measurements - Ultrasound Pulse-Wave Doppler Findings - Blood Biomarkers 2. Secondary Outcome Measures - Long-term Cardiovascular Risk Indicators
Optional Inclusion Criteria	Prospective imaging study 1- Women aged 18 or above 2- Women who are pregnant after 8 weeks 3- Women must be able to give written informed consent (ICF) Note: Women that are diagnosed with gestational hypertension (after 12 weeks) will be included. Includes the following hospital: NINEWELLS HOSPITAL	
Optional Exclusion Criteria	1- Maternal age less than 18 years 2- Women who are not capable of giving informed consent (ICF).	

Studying Pregnancy's VAscular and Retinal Changes (SPARC), Non CTIMP Protocol (SPARC) During Preg <v1.0 13/3/2025>; IRAS: 347685

5.Known retinal or eye disorders	 3- Pre-existing chronic hypertension or cardiovascular diseases diagnosed prior to the index pregnancy. 4. Women that have chronic hypertension at their booking visit (before 12 weeks)
hypertensive therapy, anticoagulants).	5.Known retinal or eye disorders6. Use of medications affecting endothelial function (e.g., ongoing anti-

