3 STUDY DESIGN

The study design is a prospective study, as it examines endothelial function in pregnant women and see how this relates to the potential development of gestational hypertension.

Study Aim: Imaging the retina in mid-stages of gestation and tracking pregnancy outcomes in correlation with serum biomarkers and for standard diagnostic measurement (ultrasound pulse-wave Doppler) imaging.

 Pregnant women will be recruited at the normal pre-natal visits (early and mid gestation scans)

- Blood samples will be taken in addition to bloods take in line with routine care (early 10-12 week scan). 20-week scan women will be requested to provide blood samples. (sFlt-1 &PLGF (clinically used to diagnose PE), endothelin-1 (marker of endothelial dysfunction))
 - Recruit women who are pregnant and follow pregnancy outcome
 - Recruit women who have gestational hypertensionGH and gestational-matched normal tensive women for CV assessment.
 - Endothelial CV assessment.
 - Retinal imaging
 - Blood sample (sFlt-1 &PLGF (clinically used to diagnose PE), endothelin-1 (marker of endothelial dysfunction))
 - Ultrasound
 - Carotid
 - Ophthalmic artery doppler

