3.3 STUDY DESCRIPTION

At the commencement of the study, the care team will approach pregnant women who meet the criteria. Pregnant women will get a Participant Information

Sheet (PIS) and can reach out to the study team if they wish to participate. Each participant is only required to attend a single visit, which will last roughly 1 hour.

Pregnant volunteers will be recruited at their first (10-12 week) and second (20 weeks) scans in line with their clinical care. In addition to their clinical ultrasounds, an ophthalmic and carotid artery ultrasound will be conducted. In addition a retinal scan and blood sample taken.

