3.4 STUDY FLOWCHART

3.5 STUDY MATRIX

Example Study Matrix

	Recruitm ent	Week 10 (+/-3wk)	Week 20 (+/-3wk)
Recruitment	V1	n/a	n/a
Cardiovascular assessment		X	X
Blood sample		X	Χ
Blood processing		X	Χ

On the same day as the blood sample, carotid artery doppler, and retinal imaging, an ophthalmic artery Doppler will be conducted. In the unlikely event that this is not possible, the ophthalmic artery doppler will be finished in 7 days.

We aim to image women up to 2 times; at 10 and 20 weeks (+/- 3 weeks) in line with their routine clinical care. However, we will accept only one visit at either of the timepoints.

STUDY ASSESSMENTS

Retinal imaging

Retinal imaging is a basic ophthalmic imaging technique which takes a photo of blood vessels at the back of the retinal. The participant needs to open her eyes and stare straight ahead at an object while the image is taken and uploaded to a computer.

Doppler Ultrasound

The ultrasound is a painless, safe test that uses sound waves to make images of the region of interest. Two regions will be examined in this study, which are Ophthalmic and Carotid region.

OPHTHALMIC ARTERY DOPPLER

The participant will be positioned in a supine position and will rest for 5 minutes. Subsequently, an ultrasound probe with sterile conduction gel will be applied to her closed upper eyelid. A quick 2D scan will be undertaken to identify anatomical features of the eye, including the optic nerve, visible as a hypoechoic band, which will be utilised as a reference. The ocular artery will be identified using colour flow, specifically in the superior and medial regions of the artery, around 15 mm behind the optic disc. Subsequently, pulsed-wave Doppler will be employed to document three to five similar waveforms.

To reduce any potential negative impact on the eyes and adhere to the ALARA ("as low as reasonably achievable") guideline, the study will be conducted in under 2 minutes per eye. Both eyes will be imaged.

CAROTID ULTRASOUND

During the test, gel is applied to the side of the neck to help the sound waves travel effectively. While lying down, a small scanner is gently placed on the skin of the neck to take the necessary pictures. This procedure is safe and may cause some pressure, but not pain, as the device moves on the neck.

The elasticity of the blood vessels will also be measured. A small pen-like device will be placed gently on the neck and at the same time a cuff is placed on the thigh (over your clothes).

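### The retinal–biomarker correlation in Section 6.2 does not hold gestational age at the scan fixed, although women may be measured at widely different gestations, so gestation can create or mask an association

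*Protocol*

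**What the plan says.** **The analysis.** Section 6.2 plans a correlational analysis "between retinal metrics and blood biomarkers to examine associations". A separate item plans multivariable regression "to control for confounding factors such as maternal age, BMI, and pre-existing health conditions". Neither item says which visit supplies the data, and neither names gestational age at measurement.

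**When women are measured.** The study matrix in Section 3.5 places the cardiovascular assessment and the blood sample at week 10 and week 20, each with a window of 3 weeks either side. It then adds: "However, we will accept only one visit at either of the timepoints". Section 3.3 says: "Each participant is only required to attend a single visit". The synopsis sets an entry criterion ("Women who are pregnant after 8 weeks") that moves the earliest scan from week 7 to about week 8.

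**Other timing statements.** The stated aim in Section 6.2, Tables 1 and 2 in Section 2, recruitment in Section 3.2 and the case criteria in Section 3.14 all refer to mid or late pregnancy. The secondary aim in Table 2 refers to early and mid gestation.

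**Control for gestation.** The only control stated is in Section 3, which calls for "gestational-matched normal tensive women for CV assessment". That concerns the comparison of women with and without gestational hypertension (GH).

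**The concern.** A correlation across women is meant to show whether those with worse retinal metrics also have worse endothelial biomarkers. If some women are measured near week 10 and others near week 20, and both measures drift over those weeks, the pooled data form two clusters displaced along both axes. The clusters alone yield a correlation, even when nothing links the two measures among women at the same gestation. If the drifts run in opposite directions, a real link can be hidden.

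Matching normotensive to GH women does not deal with this. Matching makes gestation similar in the two groups, so gestation still varies between women within each group, and a group term cannot absorb it.

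The association of retinal metrics with serum biomarkers is the hypothesis of Section 6.2 and part of the secondary objective. A shared time course of pregnancy could be read as evidence that retinal imaging tracks endothelial function.

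**Working it through.** **The plan's own figure.** The protocol gives no sample size or expected value for the correlation. Its 11 per group, and 11 / 0.10 = 110 women to recruit, belong to the group comparison in Section 6.1. I use n = 22 (analysed) and n = 110 (recruited) only as the two sample sizes that the documents offer.

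**Inputs**
- From the protocol: two windows, weeks 7–13 (about 8–13 after the entry criterion) and weeks 17–23; either visit accepted.
- Assumed: each measure shifts between week 10 and week 20 by d₁ and d₂ within-gestation SDs, over a range of 0 to 2. The documents give no slope for any retinal metric or biomarker.
- Assumed: no correlation within a visit, one visit per woman, and a two-sided 5% Pearson test. The protocol sets no significance level for this analysis.

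**Formula.** With a fraction p of women at the early visit and q = p(1 − p), the pooled correlation is

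r = q·d₁·d₂ / √[(1 + q·d₁²)(1 + q·d₂²)].

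For an even split q = 0.25, and with d₁ = d₂ = d this becomes r = (d²/4) / (1 + d²/4). At d = 1: 0.25 / 1.25 = 0.20. At d = 1.5: 0.5625 / 1.5625 = 0.36. The critical |r| is 0.423 at n = 22 and 0.187 at n = 110.

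**Rejection rates by simulation, even split, no link within visit**

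| Shift in both measures | Pooled r | n = 22, plain | n = 22, gestation or visit partialled out |
|---|---|---|---|
| 0.5 SD | 0.06 | 6% | 5% |
| 1 SD | 0.20 | 15% | 5% |
| 1.5 SD | 0.36 | 42% | 5% |
| 2 SD | 0.50 | 75% | 5% |
| 1 SD in one measure, 0 in the other | 0.00 | 5% | 5% |

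Spreading gestation uniformly over the windows, with a floor at week 8, gives nearly the same result: 6%, 16%, 44% and 77% for the first four rows. With n = 110 and 1 SD in both measures the rate is 56% at two fixed gestations and 62% with the windows. At 0.5 SD with the windows it is 10%.

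**Uneven split, n = 22.** With 4 early scans, q = (4/22)(18/22) = 0.149. At d = 1, r = 0.149 / 1.149 = 0.13. With 2 early scans, q = (2/22)(20/22) = 0.083 and r = 0.083 / 1.083 = 0.08.

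| Early scans | 1 SD in both | 1.5 SD in both |
|---|---|---|
| 11 of 22 | 15% | 41–42% |
| 4 of 22 | 9% | 21% |
| 2 of 22 | 6% | 11% |

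**One window only.** With a drift of 1 SD per 10 weeks and all scans in a single window, r is 0.02–0.03 and the rate 5–6%. The artefact comes from mixing distant gestations.

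**Masking.** Take an illustrative within-visit correlation of 0.5 and shifts of +1 and −1 SD. The pooled value is (0.5 − 0.25) / (1 + 0.25) = 0.20, below the critical 0.423 at n = 22.

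**The case against.** The strongest reply is that Section 6.2 places its aim in mid-to-late gestation, so week-10 scans may fall outside this correlation. Nowhere does the protocol say that the visits are pooled. A reader might infer that the analysis certainly mixes weeks 7 to 23 and that the measures will therefore correlate. The documents do not support that. Pooling is implied by accepting either visit and designating neither, the earliest week is about 8, and correlation through gestation is possible rather than certain. The reply does not remove the problem, however. The mid-to-late wording conflicts with the week 10/20 matrix and with the early-and-mid wording of the secondary aim. Section 6.1 also seeks measurements at the onset of GH, which Section 9.1 defines as after 20 weeks, so scans may run later than week 23 and still span many weeks.

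Three further points stand and limit the size:
- The even split is the worst case. Cases are described as mid-to-late and controls as matched on gestation, so early scans may be few among the 22.
- Rates of 42% or 75% need shifts of 1.5 or 2 SD in both measures, which nothing in the documents establishes.
- The correlation is exploratory, with no significance level of its own.

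It can also be said that the confounder list is open and that a SAP could settle the matter. That is fair as far as it goes: gestational age is not excluded. But the list belongs to the regression item. The correlation item carries no adjustment, and the omitted variable is the one that the visit rule itself makes differ between women.

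**Conclusion.** The concern holds in a limited form. The protocol lets women be measured at widely different gestations and plans a plain correlation with no designated visit and no gestational-age term. If both measures change with gestation, that correlation can be partly or wholly produced, or masked, by gestation.

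The size cannot be fixed from the documents. It rests on assumed slopes, on the split between visits, and on which women enter the analysis. It ranges from negligible (about 5% if only one measure shifts, 6% at 0.5 SD in both with 22 women) to material (15% at 1 SD and 42% at 1.5 SD with an even split). It grows if all 110 recruited women are used. The correction should be made because it removes the artefact in every scenario examined, at little cost.

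**What to change.** In Section 6.2, replace the plain correlation with a partial correlation, or a linear regression of each retinal and Doppler measure on each biomarker, that includes gestational age at the scan. Analysing each visit separately is an acceptable alternative. Use one visit per woman, or add a woman-level effect if both visits are used, since two visits from one woman are not independent. Add gestational age at the scan to the named covariates.

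In Section 5.1, list gestational age at the scan among the CRF items, where it is not now named. Reconcile the mid-to-late wording in Sections 2, 3.2, 3.14 and 6.2 with the week 10/20 matrix in Section 3.5, so that the gestations entering this analysis are clear.

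The cost is a few sentences, one CRF field and one degree of freedom. Separate analyses by visit would cost more, because each would use fewer women.
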